4.6.2. Benefit Assessment

In subjects with T2DM, treatment with albiglutide lyophilized drug product resulted in clinically relevant lowering of HbA_{1c} at both the 30 mg and 50 mg doses when given as monotherapy and in combination with metformin, sulfonylureas (SUs), thiazolidinedione or basal insulin. The durability of the effect on glycemic control was shown over a study period of up to 3 years. Consistent with its mechanism of action, albiglutide was not associated with clinically relevant hypoglycemia except when used in combination with an SU or insulin, and incidence rates with the combination were less than those reported with SUs or insulin alone. Body weight decreased slightly or remained stable during treatment, which is of benefit considering that continuous weight gain is a clinical problem in this patient group. Maintaining body weight while decreasing HbA_{1c} is therefore considered a beneficial effect of importance.

There are currently no data available for the use of the albiglutide liquid drug product in humans. Based on the current understanding of albiglutide degradation pathways and clinical outcomes from exposure to variants/impurities, similar PK, PD and clinical comparability between the liquid drug product and lyophilized drug product is expected.

4.6.3. Overall Benefit:Risk Conclusion

Taking into account the measures taken to minimize risk to subjects participating in this study, the known and potential risks identified with albiglutide are justified by the benefits that have been demonstrated in subjects with T2DM.

5. SELECTION OF STUDY POPULATION AND WITHDRAWAL CRITERIA

Specific information regarding warnings, precautions, contraindications, AEs, and other pertinent information on the GlaxoSmithKline (GSK) investigational product or other study treatment that may impact subject eligibility is provided in the IB and in the product labeling for those countries where marketing authorization for albiglutide has been granted.

Deviations from inclusion and exclusion criteria are not allowed because they can potentially jeopardize the scientific integrity of the study, regulatory acceptability or subject safety. Therefore, adherence to the criteria as specified in the protocol is essential.

5.1. Inclusion Criteria

A subject will be eligible for inclusion in this extension study only if all of the following criteria apply:

[1] TYPE OF SUBJECT

- | |
|--|
| 1. Subjects who have completed the 26 week Treatment Phase of Study 200952 |
|--|

[2] SEX

2. Male or female
3. Female subject is eligible to participate if she is not pregnant (as confirmed by a negative serum human chorionic gonadotrophin (hCG) test for females of reproductive potential only), not breastfeeding, and at least one of the following conditions applies:
 - a) Reproductive potential and agrees to follow one of the options listed in the GSK Modified List of Highly Effective Methods for Avoiding Pregnancy in Females of Reproductive Potential (FRP) (eg., combined oral contraceptive pill; see [Appendix 2](#)) from 30 days prior to the first dose of study medication and until after the last dose of study medication and completion of the follow-up visit.
 - This does not apply to FRP with same sex partners, when this is their preferred and usual lifestyle or for subjects who are and will continue to be abstinent. Other situations in which contraception in FRP may not need to be mandated should be discussed with the Medical Monitor.
 - b) Non-reproductive potential defined as either:
 - Pre-menopausal with one of the following: (i) documented tubal ligation; (ii) documented hysteroscopic tubal occlusion procedure with follow-up confirmation of bilateral tubal occlusion; (iii) hysterectomy; or (iv) documented bilateral oophorectomy, or;
 - Postmenopausal defined as 12 months of spontaneous amenorrhea and age appropriate (i.e., >50 years). In questionable cases, a blood sample with simultaneous follicle stimulating hormone (FSH) >40 mIU/mL and estradiol <40 pg/mL (<140 pmol/L) is confirmatory, depending on local laboratory ranges. Females on hormone replacement therapy (HRT) and whose menopausal status is in doubt will be required to use one of the highly effective contraception methods if they wish to continue their HRT during the study. Otherwise, they must discontinue HRT to allow confirmation of post-menopausal status prior to study enrolment.

[3] INFORMED CONSENT

4. Able and willing to provide informed consent.

5.2. Exclusion Criteria

A subject will not be eligible for inclusion in this study if any of the following criteria apply:

[1] TYPE OF SUBJECT

1. Subject meets one or more of the withdrawal stopping criteria at Visit 1 (Week 26) (see Section [5.4](#))

5.3. Hyperglycemia Rescue

During the study of diabetics, there is always the possibility of hyperglycemia which might impact subject safety. Subjects who experience persistent hyperglycemia will qualify to undergo hyperglycemia rescue. Investigators must adhere to the labeling of the US FDA-approved prescribing information or to the local labeling of the respective country for all rescue medications. The conditions for hyperglycemia rescue are defined in [Table 3](#).

Table 3 Conditions for Hyperglycemia Rescue

Time Interval on Treatment	Hyperglycemia Rescue
≥Week 26 and <Week 52	HbA _{1c} ≥8.5%

1. HbA_{1c} = glycosylated hemoglobin

Subjects can be rescued at any time. Subjects who qualify for rescue should return to the study center for a rescue visit, which includes efficacy assessments. The laboratory assessments should include safety laboratory tests (e.g., chemistry and complete blood count) and HbA_{1c}. As determined by the investigator, rescued subjects may be seen more frequently during unscheduled visits until their diabetes has stabilized. Subjects will continue in the study after rescue and will continue with their blinded study treatment until the study is completed. It is critical that subjects continue in the study after rescue in order to have complete and unbiased follow-up of long-term safety and efficacy assessments.

The rescue and uptitration criteria above should apply in the majority of circumstances; however, in the event a subject experiences significant evidence of hyperglycemia (e.g., symptoms of polyuria and polydipsia and laboratory evidence of hyperglycemia), the investigator may, based upon his or her judgment, rescue the subject with appropriate therapy at any time following randomization. Such subjects may either have rescue medication added to the existing randomly assigned study medication or, if in the judgment of the investigator (or the product labeling for rescue medications) this is not appropriate, the subject will be discontinued from study medication and appropriate rescue therapy initiated. Such subjects will continue to be followed in the study for their cardiovascular and other safety information; however, they will not receive further study medication. Rather they will be prescribed alternative therapy in order to optimize their diabetes control.

The preferred postrescue add-on treatment is insulin. Other medications may be added at the investigator's discretion. The addition of other GLP-1 analogues (exenatide or liraglutide) is prohibited as the safety of dosing with multiple GLP-1 analogues is unknown. The use of dipeptidyl peptidase-IV inhibitors is prohibited. The addition of a thiazolidinedione (rosiglitazone or pioglitazone) is discouraged.

5.4. Withdrawal/Stopping Criteria

Every effort should be made to keep subjects in the study. The reason for a subject not completing the study will be recorded in the subject's electronic case report form (eCRF).

Any subject experiencing the following will be required to discontinue investigational product and will be withdrawn from the study:

- Any AE, which, in the opinion of the investigator precludes effective participation of the subject or poses a safety concern
- The following AEs **will** require withdrawal:
 - Confirmed pancreatitis, acute or chronic.
 - Pancreatic cancer.
 - Confirmed MTC or other thyroid C-cell neoplasia.
 - Liver chemistry abnormalities exceeding the threshold criteria outlined in Section [5.4.1](#)
 - QTc abnormalities exceeding the threshold criteria outlined in Section [5.4.2](#).
 - Severe allergic/hypersensitivity reactions that are considered by the investigator to be attributable to investigational product or without a likely alternative aetiology.
- eGFR ≤ 30 mL/min/1.73 m² (calculated using the MDRD formula).
- Subject becomes pregnant or intends to become pregnant during the study.
- Need for chronic use of a prohibited concomitant medication (Section [6.10.2](#))
- Major protocol deviation (the investigator should discuss the protocol deviation with the medical monitor before withdrawing study medication)
- Subject decision (reason to be documented in the eCRF, if specified by the subject)
- Investigator discretion
- Study closed/terminated or investigator site closed (where subject transfer to another site is not possible)

The following actions must be taken in relation to a subject who fails to attend the clinic for a required study visit:

- The site must attempt to contact the subject and re-schedule the missed visit as soon as possible.
- The site must counsel the subject on the importance of maintaining the assigned visit schedule and ascertain whether or not the subject wishes to and/or should continue in the study.
- In cases where the subject is deemed 'lost to follow up', the investigator or designee must make every effort to regain contact with the subject (where possible, 3 telephone calls and if necessary a certified letter to the subject's last known mailing address or local equivalent methods). These contact attempts should be documented in the subject's medical record.

- Should the subject continue to be unreachable, only then will he/she be considered to have withdrawn from the study with a primary reason of “Lost to Follow-up”.

Subjects who discontinue active participation in the study will no longer receive study treatment. Immediately upon discontinuation from active participation in this study, these subjects should complete the assessments as per the end of treatment clinic visit and return for the post-treatment follow-up clinic visit 8 weeks later (Section 7.1). If a subject is unable or unwilling to return for the follow-up assessments, every effort will be made to follow-up with the subject.

Withdrawn subjects will not be replaced.

[figure not shown]
A subject may withdraw from study treatment at any time at his/her own request, or may be withdrawn at any time at the discretion of the investigator for safety, behavioral or administrative reasons. If a subject withdraws from the study, he/she may request destruction of any samples taken, and the investigator must document this in the site study records.

5.4.1. Liver Chemistry Stopping Criteria

Liver chemistry stopping and increased monitoring criteria have been designed to assure subject safety and evaluate liver event etiology (in alignment with the FDA premarketing clinical liver safety guidance).

[figure not shown]
<http://www.fda.gov/downloads/Drugs/GuidanceComplianceRegulatoryInformation/Guidances/UCM174090.pdf>

Phase III-IV Liver Chemistry Stopping and Increased Monitoring Algorithm

Liver Safety Required Actions and Follow up Assessments Section can be found in [Appendix 3](#).

Phase III-IV Liver Chemistry Increased Monitoring Algorithm with Continued Therapy for ALT $\geq 3x$ upper limit of normal (ULN) but $< 8x$ ULN

Liver Safety Required Actions and Follow up Assessments Section can be found in [Appendix 3](#).

5.4.1.1. Study Treatment Restart or Rechallenge

Study treatment restart or rechallenge after liver chemistry stopping criteria are met by any subject participating in this study is not allowed.

5.4.2. QTc Stopping Criteria

The QT interval corrected for heart rate according to Fridericia's formula (QTcF) *must* be used for *each individual subject* to determine eligibility for and discontinuation from the study.

The QTcF should be based on a single electrocardiogram (ECGs) obtained over a brief (e.g., 5-10 minute) recording period.

A subject who meets the following criteria will be withdrawn from the study:

- QTcF > 500 msec (or ≥ 530 ms for subjects with bundle-branch block or pacemaker)

5.5. Subject and Study Completion

A completed subject is one who has completed the 26 week treatment phase of the extension study. The end of the study is defined as the last subject's last visit.

6. STUDY TREATMENT

6.1. Investigational Product and Other Study Treatment

The term 'study treatment' is used throughout the protocol to describe any combination of products received by the subject as per the protocol design. Study treatment may therefore refer to the individual study treatments or the combination of those study treatments.

	Study Treatment
Product name:	Albiglutide liquid auto-injector
Dosage form/Delivery system:	Albiglutide liquid drug product is provided as a fixed-dose, disposable auto-injector containing albiglutide liquid drug product (50 mg) in a prefilled glass syringe with staked 29G thin-wall needle and needle shield. It is intended for single use. The cap remover is removed and the cover sleeve of the auto-injector is pressed against the skin, which results in automatic s.c. injection of the albiglutide liquid drug product. Albiglutide liquid drug product (50mg) has a pH of 5.9. The auto-injector delivers the study treatment in an injection volume of 1.0 mL for the 50 mg dose.
Unit dose strength(s) /Dosage level(s):	50mg albiglutide
Route of Administration	Subcutaneous injection in the abdomen, thigh or upper arm region. Rotation of injection sites is recommended.
Dosing instructions:	Administered as a single s.c. injection once a week on the same day each week. Administered at any time of day without regard to meals

6.2. Treatment Assignment

All subjects will receive 50 mg albiglutide liquid drug product via auto-injector.

6.3. Planned Dose Adjustments

Down-titration (dose reduction) of albiglutide from 50 mg to 30 mg is **NOT** permitted. If a subject experiences tolerability issues with the 50mg dose then the subject may be withdrawn from the study at the discretion of the investigator.

Subjects on a stable dose of metformin at the start of study 200952 may have their metformin dose adjusted during the extension study at the discretion of the investigator based on clinical need.

6.4. Blinding

This extension study will be an open-label study.

6.5. Packaging and Labeling

The contents of the label will be in accordance with all applicable regulatory requirements.

6.6. Preparation/Handling/Storage/Accountability

No special preparation of study treatment is required other than that described in Section [6.1](#).

Only subjects enrolled in the study may receive study treatment and only authorized site staff may supply and administer study treatment. All study treatments must be stored in a secure environmentally controlled and monitored (manual or automated) area in accordance with the labeled storage conditions with access limited to the investigator and authorized site staff.

The investigator, institution, or the head of the medical institution (where applicable) is responsible for study treatment accountability, reconciliation, and record maintenance (i.e. receipt, reconciliation and final disposition records).

Further guidance and information for final disposition of unused study treatment are provided in the Study Reference Manual (SRM).

Under normal conditions of handling and administration, study treatment is not expected to pose significant safety risks to site staff. Take adequate precautions to avoid direct eye or skin contact and the generation of aerosols or mists. In the case of unintentional occupational exposure notify the monitor, Medical Monitor and/or GSK study contact.

A Material Safety Data Sheet (MSDS)/equivalent document describing occupational hazards and recommended handling precautions either will be provided to the investigator, where this is required by local laws, or is available upon request from GSK.

6.7. Compliance with Study Treatment Administration

The subject or designee will administer study treatment at the time points specified in the Time and Events Table (Section 7.1).

Subjects will be instructed to return all unused and used auto-injectors at the visits specified in the Time and Events Table (Section 7.1) in order to perform drug accountability and determine compliance. In addition, subjects will be provided with a pre-printed card at each dispensing visit to record the date of each dose. The card is to be returned at the next dispensing visit.

6.8. Treatment of Study Treatment Overdose

No data are available with regard to albiglutide overdose in humans. The highest recommended dose of albiglutide is 50 mg once weekly.

During clinical studies of subjects with T2DM, the highest dose of albiglutide administered was 100 mg subcutaneously every four weeks for 12 weeks. This dose was associated with an increased frequency of nausea, vomiting, and headache.

There is no specific antidote for overdose with albiglutide. In the event of a suspected overdose, the appropriate supportive clinical care should be instituted, as dictated by the subject's clinical status. Anticipated symptoms of an overdose may be severe nausea, vomiting or headache. A prolonged period of observation and treatment for these symptoms may be necessary, taking into account the half-life of albiglutide (5 days).

6.9. Treatment after the End of the Study

Following completion of the Week 52 visit, subjects will return to the study centre in 8 weeks for the post-treatment follow-up visit (Week 60 visit) and will complete the study.

Investigational product will not be provided to subjects by GSK after the end of the study.

The investigator is responsible for ensuring that consideration has been given to the post-study care of the subject's medical condition, whether or not GSK is providing specific post-study treatment.

The half-life of albiglutide is approximately 5 days, and significant therapeutic concentrations can persist for 3 to 4 weeks after discontinuation. The choice of other medicinal products and dose selection should be considered accordingly, as adverse reactions may continue and efficacy may, at least partly, persist until albiglutide levels decline.

6.10. Concomitant Medications and Non-Drug Therapies

All medications taken at any time from Visit 1 (Week 26) to the follow-up visit will be recorded in the eCRF. The minimum requirement is that drug name and the dates of administration are to be recorded.

6.10.1. Permitted Medications and Non-Drug Therapies

Unless specified as a prohibited medication in Section 6.10.2, all concomitant medications should be considered permitted provided they are not contraindicated in the albiglutide Prescribing Information or for the individual subject concerned. Although stable doses of all concomitant medications are preferable, changes in medications during the study to appropriately treat clinical conditions that might arise are allowed.

Like other members of the class, albiglutide causes a delay in gastric emptying, and thereby has the potential to impact the absorption of concomitantly administered oral medications. This should be taken into account by investigators when prescribing concomitant medication.

Investigators must adhere to the local labeling of the respective country (e.g., the Summary of Product Characteristics (SmPC) in relevant European countries or the FDA-approved prescribing information) for all permitted medications.

6.10.2. Prohibited Medications and Non-Drug Therapies

Subjects must not use any of the following medications:

- Dipeptidyl peptidase-IV inhibitors and GLP-1R agonists (except albiglutide liquid drug product taken as study treatment) are prohibited.
- Any investigational drug other than study treatment (albiglutide liquid drug product).
- Oral or systemically injected corticosteroids (inhaled, intra-articular, epidural, and topical corticosteroids are allowed); short courses of oral steroids (single dose or multiple doses for up to 7 days) may be permitted provided these cases are discussed with the medical monitor

If a subject receives a prohibited medication, a protocol deviation will be reported and continuation in the study will be discussed with and agreed upon by the medical monitor.

7. STUDY ASSESSMENTS AND PROCEDURES

Protocol waivers or exemptions are not allowed with the exception of immediate safety concerns. Therefore, adherence to the study design requirements, including those specified in the Time and Events Table, are essential and required for study conduct.

This section lists the procedures and parameters of each planned study assessment. The exact timing of each assessment is listed in the Time and Events Table Section 7.1.

Supplementary study conduct information not mandated to be present in this protocol is provided in the accompanying SRM. The SRM will provide the site personnel with administrative and detailed technical information that does not impact subject safety.

7.1. Time and Events Table

Procedure	Extension Study Visit Study Week	Treatment					¹¹ End of Treatment	Follow-up ¹²
		1	2	3	4	5	6	7
		26 ¹³	30	36	42	48	52	60
Informed consent for Study 204682	X							
Inclusion/exclusion criteria review ¹	X							
Full (F) or brief (B) physical exam ²	F	B	B	B	B	F	F	
Weight	X	X	X	X	X	X	X	
12-lead ECG ³	X					X	X	
Vital signs	X	X	X	X	X	X	X	
Serum (S)/Urine (U) pregnancy test (WCBP)	S	U	U	U	U	S		
Clinical chemistry/hematology samples ⁴	X	X	X		X	X	X	
Lipids (including total cholesterol, LDL-C, HDL C, triglycerides, FFAs) ⁴	X					X	X	
Urinalysis ⁵	X					X		
HbA _{1c} ^{6,7}	X	X	X	X	X	X	X	
FPG ⁷	X	X	X	X	X	X	X	
eGFR	X		X		X			
Immunogenicity sample ⁸	X	X	X			X	X	
Review AE/SAE, concomitant medication and hypoglycemia events	X	X	X	X	X	X	X	
Advice on diet and exercise ⁹	X	X	X	X	X	X		
Subject Experience / Satisfaction Exit Questionnaire						X		
Study treatment dispensed	X	X	X	X	X			
Study treatment compliance ¹⁰		X	X	X	X	X		

WCBP: Women of child bearing potential; FFA: free fatty acids; LDL-c: low density lipoproteins cholesterol; HDL-c: high density lipoproteins cholesterol

- Before dosing**, the investigator must review **all** inclusion and exclusion criteria to confirm subject's eligibility. If a subject no longer meets all of the eligibility criteria (e.g., there is evidence of a new MI on an ECG or ALT, etc. are out of range), **do not administer the study treatment** and contact the medical monitor to discuss how to proceed (e.g., to determine if repeat testing is warranted).
- Details of full and brief physical examinations are provided in Section [7.3.3](#).
- 12-lead ECGs will be obtained **before** measurement of vital signs and collection of blood samples for laboratory testing. See Section [7.3.5](#).
- Clinical chemistry and hematology assessments are described in Section [7.3.6](#).

5. Urine samples should be collected in the early morning.
6. Blood samples for HbA_{1c} should be collected before administration of study treatment.
7. Subjects will have their FPG and HbA_{1c} levels evaluated to monitor for potential hyperglycemia.
8. Blood samples for immunogenicity are to be collected **before** study drug administration.
9. Standard diabetic dietary and exercise advice will be reinforced through the end-of-treatment visit.
10. Compliance will be assessed as described in Section 6.7.
11. Subjects who discontinue study treatment should be handled as described in Section 5.4.
12. Follow-up visit for subjects who have discontinued study treatment (see Section 5.4) or subjects who have completed the 52 week treatment period.
13. Visit 1 of 204682 is also the end of treatment visit in Study 200952.
14. Visit 1 of Study 204682; albiglutide liquid drug product administered to all study subjects.

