4.2. Treatment Arms and Duration

- This extension study will comprise 2 study periods (Figure 1): treatment (26 weeks) and post-treatment follow-up (8 weeks).
- All subjects will receive 50 mg albiglutide liquid drug product via auto-injector.
- Study treatment will be administered once weekly by s.c. injection in the abdomen, thigh, or upper arm.
- The first dose of study treatment will be administered by the subject during the clinic visit (Visit 1, Week 26) with supervision from clinic staff. All further doses of study treatment will be self-administered by the subject.
- During the study, any potential events of pancreatitis will be adjudicated by an independent pancreatitis adjudication committee (PAC) (Section 10.8).

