7.2. Screening and Critical Baseline Assessments

Before any study-specific procedure is performed, valid informed consent and assent as appropriate must be obtained.

Full details of assessments undertaken at Visit 1 (Week 26) are provided in the Time and Events Table Section 7.1.

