7.3.6. Clinical Safety Laboratory Assessments

All protocol required laboratory assessments, as defined in [Table 4](#) must be conducted in accordance with the Laboratory Manual, and Protocol Time and Events Schedule in

Section 7.1. Laboratory requisition forms must be completed and samples must be clearly labeled with the subject number, protocol number, site/centre number, and visit date. Details for the preparation and shipment of samples will be provided by the laboratory and are detailed in the laboratory manual. Reference ranges for all safety parameters will be provided to the site by the laboratory responsible for the assessments.

If additional non-protocol specified laboratory assessments are performed at the institution's local laboratory and result in a change in subject management or are considered clinically significant by the investigator (e.g., SAE or AE or dose modification), the results must be recorded in the eCRF.

Refer to the SRM for appropriate processing and handling of samples to avoid duplicate and/or additional blood draws.

All study-required laboratory assessments will be performed by a central laboratory. The results of the test must be entered into the eCRF.

Hematology, clinical chemistry, urinalysis and additional parameters to be tested are listed in [Table 4](#).

Table 4 Protocol Required Safety Laboratory Assessments

Laboratory Assessments	Parameters			
Hematology	Platelet Count	RBC Indices:		WBC count with Differential:
	RBC Count	mean corpuscular volume (MCV)		Neutrophils
	Hemoglobin	mean corpuscular hemoglobin (MCH)		Lymphocytes
	Hematocrit			Monocytes
				Eosinophils
				Basophils
Clinical Chemistry ¹	blood urea nitrogen (BUN)	Potassium	Aspartate amino transferase (AST (SGOT))	Total and direct bilirubin
	Creatinine	Sodium	ALT (SGPT)	Total Protein
	Calcium	chloride	Alkaline phosphatase	Albumin
	bicarbonate	Uric acid	Gamma glutamyl transferase (GGT)	
Routine Urinalysis	
 • Specific gravity • pH, glucose, protein, blood and ketones by dipstick • Microscopic examination (if blood or protein is abnormal) 			
Other Laboratory Tests	
 • HbA_{1c} • FPG • Lipids including total cholesterol, LDL-C, HDL C, triglycerides, FFAs (fasting) ² • FSH and estradiol (as needed in women of non-child bearing potential only) • Serum or urine hCG Pregnancy test (as needed for women of child bearing potential) 			

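### The first dose is fixed at Visit 1, but the serum pregnancy test it depends on is first scheduled at that visit and run centrally, so women may be dosed with no result from this study in hand

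*Protocol*

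**What the plan says.** Several rules in the Protocol meet at Visit 1 (Week 26).

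- **Dose timing.** Section 4.2: "The first dose of study treatment will be administered by the subject during the clinic visit (Visit 1, Week 26"), supervised by clinic staff. Footnote 14 of Section 7.1 says of the same visit: "albiglutide liquid drug product administered to all study subjects".
- **Check before dosing.** Footnote 1 of Section 7.1 has the investigator go through all criteria before dosing. It continues "If a subject no longer meets all of the eligibility criteria (e.g., there is evidence of a new MI on an ECG or ALT" and similar values being abnormal). In that event drug is withheld and the medical monitor is contacted, among other things about repeat testing.
- **Criteria that need a laboratory.** Inclusion 3 (Section 5.1) requires a negative serum hCG in females of reproductive potential. Exclusion 1 (Section 5.2) applies the Section 5.4 stopping criteria at Visit 1. These include eGFR at or below 30 mL/min/1.73 m² and the liver thresholds of Section 5.4.1 and Appendix 3.
- **When samples are drawn.** The row "Serum (S)/Urine (U) pregnancy test (WCBP") shows serum at Visit 1, urine at Visits 2 to 5 and serum again at Visit 6. Chemistry and eGFR also start at Visit 1. Consent for this study is taken at Visit 1, and Section 7.2 says: "Before any study-specific procedure is performed, valid informed consent and assent as appropriate must be obtained".
- **Where tests are run.** Section 7.3.6: "All study-required laboratory assessments will be performed by a central laboratory". It adds: "Details for the preparation and shipment of samples will be provided by the laboratory". A site's local laboratory appears only in a sentence on extra tests, which opens "If additional non-protocol specified laboratory assessments are performed at the" and gives them no role in eligibility.
- **Safeguard relied on.** Table 2 (Section 4.6.1) lists a negative pregnancy test before entry as mitigation for fetal risk and reports embryofetal lethality in mice.

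**The concern.** Pregnancy status is meant to be known before anyone is dosed. As scheduled, the only pregnancy test on the first-dose day is a serum sample that leaves the site. A site that keeps to Section 4.2 may therefore give the dose before the result exists, and the safeguard in Table 2 would not operate at entry. Sections 5 and 7 leave little room for improvisation: the first allows no eligibility deviations, the second no waivers except for immediate safety concerns.

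The same ordering applies to eGFR and liver chemistry. The stakes there are lower, because subjects have just completed 26 weeks of treatment in a study comparing two albiglutide products.

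Footnote 1 also offers an out-of-range ALT as an example of lost eligibility. That is not the threshold Section 5.2 applies.

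**Working it through.** The Protocol gives no figure on this point to reproduce. The check is of the order of events, then of the exposure involved.

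**1. What is known when the dose is given**

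| Check at Visit 1 | Source | Available on site? |
|---|---|---|
| QTcF, other ECG findings | Sections 5.4.2, 7.3.5 | Yes, the ECG is recorded on site |
| Clinical review | Section 5.4 | Yes |
| Serum hCG | Section 5.1 | Only if the central result returns within the visit |
| eGFR | Sections 5.4, 7.3.7 | As above |
| ALT, bilirubin | Section 5.4.1, Appendix 3 | As above |

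With consent at Visit 1, none of the last three can be drawn earlier as a procedure of this study.

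**2. Doses given before results are known**

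Dosing is weekly, so doses fall on days 0 and 7 after Visit 1. With turnaround *t* in days, doses given before the result = 1 + floor(*t*/7) for *t* > 0. Turnaround is not stated. Assuming *t* = 1 to 6, floor(*t*/7) = 0, so one dose (50 mg) is given. If results return within the visit, none is. How many pregnant women would be dosed cannot be estimated: the Protocol gives a maximum of 300 subjects but no number of women of child-bearing potential.

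**3. Would holding the first dose for up to 3 days be better?**

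Half-life is 5 days (Sections 6.8 and 6.9). Pre-dose level after a delay of *d* days, relative to the usual 7-day trough, is 2^(−*d*/5). The 26th weekly dose falls on day *d* + 25×7, and the Week 52 visit on day 26×7 = 182. The last parent-study dose is assumed to be 7 days before Visit 1, which is not shown.

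| *d* | Level relative to trough | Day of 26th dose |
|---|---|---|
| 1 | 2^(−1/5) = 0.87 | 176 |
| 2 | 2^(−2/5) = 0.76 | 177 |
| 3 | 2^(−3/5) = 0.66 | 178 |

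Drug level and schedule would tolerate a hold. But under the assumed 1 to 6 days, results arriving on days 4, 5 or 6 fall outside a 3-day limit and the problem returns. Every subject who waits also needs another supervised visit. A hold is therefore the weaker remedy.

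**4. The ALT example**

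Under Appendix 3, a subject with ALT from 3 to below 8×ULN, bilirubin below 2×ULN and no related symptoms, who can be monitored weekly, may stay on treatment. An ALT that is merely abnormal is therefore not by itself a Section 5.4 stopping criterion, nor an exclusion under Section 5.2.

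**The case against.** A reader might infer that the Protocol sets rules no site can follow together, and that all first doses must wait for central results. The documents do not support that.

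- **Turnaround is not stated.** Results back within the visit would remove the problem, and the laboratory manual is not shown. The Study Reference Manual is not shown either, though Section 7 limits it to matters that do not affect subject safety.
- **A parent-study sample may exist.** Visit 1 is also the end-of-treatment visit of Study 200952, and inclusion 3 does not date the serum hCG. An earlier result under that consent is possible, though nothing shown says it counts. Exclusion 1, by contrast, is tied to Visit 1.
- **Footnote 1 already settles a known failure.** Drug is withheld and the medical monitor is contacted. Only a pending result is uncovered, and a site that waits is following a specific safety instruction.
- **The added exposure is incremental.** A pregnancy present at Visit 1 has generally been exposed to albiglutide already, and Section 6.9 says therapeutic levels can last 3 to 4 weeks after stopping. Inclusion 3 also asks for highly effective contraception starting 30 days before dosing, with exceptions.
- **Urine hCG is itself in Table 4.** Read literally, Section 7.3.6 would send that test to the central laboratory too.
- **The ALT wording is an example.** It leads to a call, and Section 5.4 includes investigator discretion.

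Most of this stands. It reduces the point to pending results, chiefly the pregnancy test, and makes the ALT wording a minor correction. It does not explain why the first-dose day has no on-site pregnancy test when urine tests are scheduled at Visits 2 to 5.

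**Conclusion.** The point holds in a limited form. Unless the central serum hCG returns within Visit 1, following Section 4.2 means dosing women of child-bearing potential with no pregnancy result from this study, contrary to the intent of footnote 1 and Table 2. This rests on two assumptions: results take longer than the visit, and no parent-study result is accepted in their place. With turnaround of 1 to 6 days the avoidable exposure is one 50 mg dose per affected woman; their number cannot be estimated.

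For eGFR and liver values the gap is the same but the risk is small, about one further weekly dose after 26 weeks on albiglutide. It does not justify delaying every first dose. No endpoint, analysis or sample size is affected. This is an inexpensive safety improvement, not a flaw in the study's inference.

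**What to change.** 1. **On-site pregnancy test.** In Section 7.1 change the Visit 1 pregnancy cell from S to S, U. Require a negative on-site urine hCG before the first dose, with the central serum test as confirmation. State in Section 7.3.6 that urine hCG is done on site.
2. **Rule for pending results.** State in footnote 1 that the Visit 1 dose may be given on the on-site checks (urine hCG, ECG, clinical review) while central results are pending. Those results must be reviewed before the second weekly dose, and treatment stops if serum hCG is positive or an eGFR or liver stopping criterion is met. Refer to this rule from inclusion 3 and exclusion 1, so that such a dose is not an eligibility deviation under Section 5.
3. **ALT example.** In footnote 1 replace the reference to abnormal ALT and similar values with: a stopping criterion in Section 5.4, 5.4.1 or 5.4.2 is met.

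Cost: one urine test per woman of child-bearing potential, at a visit where urine is already collected, plus the wording changes. No extra blood draw or visit is needed. What remains is that a subject who fails on a central eGFR, liver or serum hCG result will have had one dose; she or he then counts in the Safety Population as now defined.
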